6.14.6. Standardized Growth

Weight, height, and BMI data will be merged to the Centers for Disease Control and Prevention (CDC) standard growth data (released in 2000) by age and gender in order to compare patients’ growth with the standard. Z-score and standardized percentile of weight, height, and BMI at each visit will be calculated and compared to the 2000 CDC growth charts.

The z-score and percentile calculations are based on algorithms and data provided by the National Center for Health Statistics. The details are provided in the CDC website (<https://www.cdc.gov/nccdphp/dnpao/growthcharts/resources/sas.htm>).

The following summaries will be provided for All Ixekizumab Safety Population:

- Baseline, endpoint and mean change of actual measure, z-score and standardized percentile of weight, height, and BMI will be summarized by month of ixekizumab exposure..
- Patient’s mean weight, height, and BMI standardized percentile will be plotted versus ixekizumab exposure time.

By-patient listings of actual measures, z-scores, standardized percentiles in weight height, BMI for each visit will be provided.

6.14.7. Children’s Depression Rating Scale, Revised (CDRS-R)

The Children's Depression Rating Scale–Revised (CDRS-R) (Poznanski and Mokros 1996) is the most widely used rating scale for assessing severity of depression and change in depressive symptoms for clinical research studies in children and adolescents with depression.

The CDRS-R was originally developed as a rating scale for children aged 6 to 12 years. It is a 17-item scale, with items ranging from 1 to 5 or 1 to 7 (the total score is the sum of the 17 items

and ranges from 17-113, with higher scores indicating more depressive symptoms) and is rated by a clinician via interviews with the child and parent or legal guardian. A score of ≥ 40 is indicative of depression, whereas, a score ≤ 28 is often used to define remission (minimal or no symptoms) (Mayes et al. 2010).

Change from baseline to each postbaseline visits in CDRS-R total score will be analyzed using MMRM methods for P2 Main Study Safety Population.

A shift table will be produced showing the number and percentage of patients shifting from maximum baseline score to a maximum postbaseline score in categories of ≤ 28 , >28 and <40 , and ≥ 40 for P2 Main Study Safety Population and All Ixekizumab Safety Population.

By-patient listing of CDRS-R data will be provided.

6.14.8. Columbia-Suicide Severity Rating Scale (C-SSRS)

The Columbia-Suicide Severity Rating Scale (C-SSRS) is an assessment tool that evaluates suicidal ideation and behavior. Information on the C-SSRS scale can be found through the following link: <http://www.cssrs.columbia.edu>.

Specifically, the following outcomes are C-SSRS categories and have binary responses (yes/no). The categories have been re-ordered from the actual scale to facilitate the definitions of the composite and comparative endpoints, and to enable clarity in the presentation of the results.

Category 1 – Wish to be Dead

Category 2 – Non-specific Active Suicidal Thoughts

Category 3 – Active Suicidal Ideation with Any Methods (Not Plan) without Intent to Act

Category 4 – Active Suicidal Ideation with Some Intent to Act, without Specific Plan

Category 5 – Active Suicidal Ideation with Specific Plan and Intent

Category 6 – Preparatory Acts or Behavior

Category 7 – Aborted Attempt

Category 8 – Interrupted Attempt

Category 9 – Actual Attempt (non-fatal)

Category 10 – Completed Suicide

Self-injurious behavior without suicidal intent is also a C-SSRS outcome (although not suicide-related) and has a binary response (yes/no).

Composite endpoints based on the above categories are defined below.

- **Suicidal ideation:** A “yes” answer at any time during treatment to any 1 of the 5 suicidal ideation questions (Categories 1-5) on the C-SSRS.
- **Suicidal behavior:** A “yes” answer at any time during treatment to any 1 of the 5 suicidal behavior questions (Categories 6-10) on the C-SSRS.
- **Suicidal ideation or behavior:** A “yes” answer at any time during treatment to any 1 of the 10 suicidal ideation and behavior questions (Categories 1-10) on the C-SSRS.

The Self-Harm Supplement Form is a 1-question form that is completed, at any visit, including baseline visit, that asks for the number of suicidal behaviors, possible suicidal behaviors, or nonsuicidal self-injurious behaviors the patient has experienced since the last assessment. For each unique event identified, a questionnaire (Self-Harm Follow-up Form) which collects supplemental information on the self-injurious behavior is to be completed.

Given that few or no suicidal ideation or behaviors are anticipated, C-SSRS will be listed by patient and visit. Only patients that show suicidal ideation/behavior or self-injurious behavior without suicidal intent will be displayed (that is, if a patient's answers are all "no" for the C-SSRS, then that patient will not be displayed). However, if a patient reported any suicidal ideation/ behavior or self-injurious behavior without suicidal intent at any time point, then all his/her ideation and behavior will be displayed, even if not positive. Note that missing data should not be imputed.

The Self-Harm data will be listed by patient and visit if number of events on Self-Harm Supplement Form is not zero in the eCRF Self Harm Questionnaire Supplement.

6.14.9. *Tanner Stage Scale*

The Tanner Stage Scales are a series of line drawings that are designed to aid the investigator in appropriately assessing the sexual maturity of the subject. Data gathered will be assessed to determine that no pubertal disruption has occurred during the study. Although the line drawings were originally intended for child self-assessment, evidence suggests that pubertal assessment by the child or the parents/legal guardian is not a reliable measure of exact pubertal staging, and should be augmented by a physical examination (Rasmussen et al. 2015). The drawings will be used by the dermatologist investigator as an aid.

Shift table will be produced showing the number and percentage of patients shifting from the highest stage score at baseline to the highest postbaseline stage score by gender for each scale item for All Ixekizumab Safety Population.

A by-patient listing of Tanner stage data will be provided.

6.14.10. *Immunization*

A by-patient listing of all immunization data will be provided. The listing will include any TEAEs occurring within 30 days after the vaccinations.

6.14.11. *Immunogenicity*

6.14.11.1. *Definitions and Terms*

[figure not shown]
The following sample- and patient-related definitions and parameters will be used to describe the immunogenicity data.

6.14.11.1.1. *Sample Category Definitions*

Samples are classified into the following categories:

- **Unevaluatable sample:** Sample could not be tested for ADA due to sample loss, mishandling, or errors in collection, processing, storage, and so on.
- **Anti-drug antibody (ADA) Positive sample:** The presences of ADA is detected and confirmed. The samples are reported as positive. If the sample is positive, a titer value is reported.
- **Neutralizing anti-drug antibody (NAb) Positive sample:** NAb are reported as detected.
- **Anti-drug antibody (ADA) Negative sample:** The presence of ADA is not detected and the assay drug tolerance level is not exceeded.
- **NAb Negative sample:** The presence of NAb is not detected and the assay drug tolerance level is not exceeded.
- **Inconclusive sample:** ADA/NAb is not detected in a sample, but the drug is present in the same sample at a level that can cause interference in the ADA/NAb detection method. The negative ADA/NAb result cannot be confirmed, and the sample was considered inconclusive.
 - Confirmation of a negative ADA result was based on expected ixekizumab concentrations based on PK modeling.
 - Confirmation of negative NAb results was based on ixekizumab concentrations.

Figure RHCD.6.1 illustrates the relationship of some of the above terms.

Abbreviation: ADA = anti-drug antibody.

[figure not shown]
Figure RHCD.6.1. Sample definitions.

6.14.11.1.2. Patient Category Definitions

The following categories are applied to patients, based on the classification of their samples:

- **Unevaluable patient:** a) a patient with no evaluable baseline sample and/or no evaluable postbaseline samples; b) a patient with an evaluable baseline sample, but no evaluable postbaseline sample; c) a patient with no evaluable baseline sample, but whose evaluable postbaseline values are all ADA-positive or a mix of positive and negative. Note: If all postbaseline samples are negative, the patient is considered “evaluable” and will be classified as ADA-negative.
- **Evaluable patient:** a) Patient with an evaluable baseline sample and at least 1 evaluable postbaseline sample (that is, sample after administration of study drug); b) patient with no evaluable baseline sample whose evaluable postbaseline samples are all ADA negative.

Figure RHCD.6.2 illustrates the relationship of the above terms.

Abbreviation: ADA = anti-drug antibody.

Figure RHCD.6.2. Patient categories (evaluable/unevaluable) based on sample status at baseline and postbaseline.

6.14.11.1.3. Definitions for Clinical Interpretation of Assay Results

- Baseline:** For immunogenicity analyses during Period 2, baseline is the last nonmissing observation on, or prior to, the date of the first injection of study treatment of ixekizumab (Week 0). Unless, otherwise, specified, the baseline for Overall Ixekizumab Treatment Period (Period 2, 3, and 4 combined) is defined as the last nonmissing observation on, or prior to, the date of first injection of ixekizumab. For patients originally randomized to ixekizumab during Period 2, baseline is the last nonmissing observation on, or prior to, the date of the first injection of study treatment for Period 2 (Week 0). For patients who are not originally randomized to ixekizumab in Period 2, baseline is the last nonmissing observation on, or prior to, the date of the first injection of ixekizumab (see [Table RHCD.6.10](#) for further details).

Table RHCD.6.10. Baseline Definition for Immunogenicity Analyses for Overall Ixekizumab Treatment Period

[figure not shown]
Treatment Assignment for Double-Blind Treatment Period (Period 2)	Treatment Assignment for Maintenance Period (Period 3) and Extension Period (Period 4) or Period 3 Only (Protocol Addendum RHCD[2])	Treatment Assignment for 48-Week Double-Blind, Randomized Withdrawal Period (Protocol Addendum RHCD[2] Period 4)	Baseline for Overall Ixekizumab Treatment Period Analysis ^a
Ixekizumab	Ixekizumab	NA	Week 0
Placebo	Ixekizumab	NA	Week 12
Ixekizumab	Ixekizumab	Ixekizumab	Week 0
Ixekizumab	Ixekizumab	Placebo	Week 0
Etanercept	Ixekizumab	Ixekizumab	Week 20
Etanercept	Ixekizumab	Placebo	Week 20
Placebo	Ixekizumab	Ixekizumab	Week 12
Placebo	Ixekizumab	Placebo	Week 12

Abbreviations: NA = not applicable.

^a Last non-missing observation on, or prior to, the date of the first injection of study treatment at the defined week.

- Baseline ADA-positive (preexisting antibody):** ADA detected in a sample collected at baseline.
- Baseline ADA-negative:** ADA is not detected in a sample collected at baseline.
- Treatment-emergent-(TE-) ADA positive:** a) a patient with a ≥ 4 -fold increase over a positive baseline antibody titer (Tier 3); or b) for a negative baseline titer, a patient with an increase from the baseline to a level of $\geq 1:10$.
- TE-ADA inconclusive:** A patient without a TE-ADA positive sample and with at least 1 sample for which drug levels may interfere with the ADA assay.
- TE-ADA negative:** A patient who is evaluable for TE-ADA and is not either TE-ADA positive or TE-ADA inconclusive.

Figure RHCD.6.3 illustrates the relationship of some of these terms.

Abbreviation: ADA = anti-drug antibody.

Figure RHCD.6.3. Relationship of terms for clinical interpretation of assay results for evaluable patients.

- **Incidence of TE-ADA:** Patients with TE-ADA as a proportion of the evaluable patient population during the treatment period. This excludes unevaluable patients.
- **Follow-up-emergent ADA:** ADA is first detected during the follow-up period, after study drug administration is discontinued. This category includes patients negative at baseline who increased to $\geq 1:10$ titer (4-fold increase/ 2 dilutions) after baseline in the follow-up period or patients ADA positive at baseline and increased at least 4-fold (2 dilutions) over baseline for the first time in the follow-up period.
- **Incidence of follow-up emergent ADA:** Patients with follow-up-emergent ADA as a proportion of the follow-up evaluable patient population. This excludes unevaluable patients.

All ADA positive samples will be evaluated for NAb. Definitions for NAb patient status will be defined as follows:

- **NAb-positive:** A patient where a NAb positive result is detected for ≥ 1 TE-ADA positive samples.
- **NAb-inconclusive:** A patient without a NAb positive sample and with at least 1 sample for which drug levels may interfere with the NAb assay.
- **NAb-negative:** A patient who is evaluable for NAb and is not either NAb positive or NAb inconclusive.

A flow chart that reflects the connection between the analytical test results and the clinical interpretation based on the definitions is shown in [Figure RHCD.6.4](#).

[figure not shown]

Figure RHCD.6.4. Flow chart of ADA assessment with clinical interpretation of the various result possibilities.

6.14.11.2. Immunogenicity Analyses

Immunogenicity evaluable patients will be identified as TE-ADA positive, TE-ADA negative, or TE-ADA inconclusive, according to the definitions provided in Section 6.14.11.1.2 and further grouped into TE-ADA status groups and time-varying TE-ADA status groups:

TE-ADA Status Groups:

- TE-ADA status (positive, negative, or inconclusive)
- NAb status (positive, negative, or inconclusive) for TE-ADA positive patients
- TE-ADA titer groups for TE-ADA positive patients:
 - Low Titer: TE-ADA titer value (LOCF) <1:160
 - Moderate Titer: TE-ADA titer value (LOCF) ≥1:160 and <1:1280
 - High Titer: TE-ADA titer value (LOCF) ≥1:1280

Time-Varying TE-ADA Status Groups:

Individual ADA samples will be ascribed into 3 different dichotomous variables as explained in [Table RHCD.6.11](#). Each variable has possible values of a “greater-TE-ADA status” or a “lesser-TE-ADA status,” in the sense that the level of TE-ADA detected in the greater-TE-ADA category is higher than in the lesser-TE-ADA category.

Table RHCD.6.11. TE-ADA Status Dichotomous Variables for AE Analysis

TE-ADA Status Dichotomous Variable	Greater-TE-ADA Status	Lesser-TE-ADA Status
TE-ADA positive	TE-ADA positive	not TE-ADA positive
TE-ADA moderate-to-high	TE-ADA positive with moderate titer or high titer	not TE-ADA positive, or TE-ADA positive with low titer
TE-ADA high status	TE-ADA positive with high titer	not TE-ADA positive, or TE-ADA positive with low or moderate titer

Abbreviations: TE-ADA = treatment-emergent antidrug antibodies/

Note: for purpose of this analysis, TE-ADA Inconclusive is taken to be “not TE-ADA positive.” A TE-ADA low is defined as a TE-ADA positive with a titer value <1:160; a TE-ADA moderate is defined as a TE-ADA positive with a titer value ≥1:160 and <1:1280; and a TE-ADA high is defined as a TE-ADA positive with a titer value ≥1:1280.

For each TE-ADA status dichotomous variable, a time-varying TE-ADA status will be computed. At time *t*, the TE-ADA status is taken to be the highest of the TE-ADA values bracketing time *t*. More formally, the TE-ADA status at time *t* is given by the greater of: (a) the TE-ADA status at the most-recent postbaseline measurement prior to *t*; and (b) the TE-ADA status at the first TE-ADA postbaseline measurement at or after time *t*. In this computation, “greater” is given by the greater-TE-ADA status of [Table RHCD.6.11](#). If there is no value satisfying criterion (a), then the value (b) is used. Similarly, if there is no value (b), then the value (a) is used.

For each TE-ADA status dichotomous variable, patients will be categorized according to whether they were: (1) always in lesser-TE-ADA status postbaseline; or (2) at some point postbaseline, were in greater-TE-ADA status.

6.14.11.2.1. Analyses of Characteristics of ADA Immune Response

The analyses of ADA effects will be conducted on all evaluable patients within the defined Safety Population for Period 2, All Ixekizumab Population for Combined Treatment Period (Period 2, 3, and 4 combined), and Follow-Up Population for Period 5.

The overall frequency and percentage (incidence) of patients will be summarized for the TE-ADA status groups and the time-varying TE-ADA status groups. Scheduled visits, unscheduled visits, and repeat measurements will be included.

The time to the development of TE-ADAs (TE-ADA positive, low titer, moderate titer, high titer, and NAb positive) will be calculated as follows:

Time to development of TE-ADAs/NAb (in weeks) = (Date of development of TE-ADAs/NAb – Date of first injection of study treatment + 1) / 7.

If a patient has not developed TE-ADAs/NAbs, he/she will be censored at the date of the last immunogenicity assessment. If a patient does not have any postbaseline assessments for immunogenicity, he/she will be censored at the date of randomization.

Descriptive statistics, including 25th percentile, 50th percentile (median), 75th percentile, and corresponding 95% CIs, as well as probability of TE-ADA/NAb positive by endpoint summarized by treatment group, will also be provided if sufficient data is present. A Kaplan-Meier plot of the time to development of treatment-emergent ADA/NAb will be presented by treatment group, also if sufficient data is present. Caution should be exercised in the interpretation of time-to-event analyses and related statistics, given the limited sampling scheme for immunogenicity testing.

For each TE-ADA status dichotomous variable (as defined in [Table RHCD.6.11](#)), summaries will be provided of the total postbaseline time in the greater-TE-ADA status for patients who were at some point postbaseline in the greater-TE-ADA status group. Postbaseline time in greater-TE-ADA status for each patient will be aggregated.

A by-patient listing to include treatment, visit date, visit, ADA result, TE-ADA result, NAb result, ADA titer value, ixekizumab concentration, and ADA and NAb inconclusive results will also be provided, for patients with any one sample of ADA (or NAb) positive or inconclusive.

6.14.11.2.2. Analyses of Treatment-Emergent ADA Effects on Efficacy

Efficacy analyses for Period 2 will be conducted on all evaluable patients within the ITT Population.

Analyses will be performed to examine how patient TE-ADA effects PASI 75 and sPGA(0,1) response rates at week 12 with NRI by the TE-ADA status groups as described in [Section 6.14.11.1.2](#).

A logistic regression model with treatment group, TE-ADA status and the interaction of treatment group-by-TE-ADA status included as factors will be used to test the interaction of treatment group -by-TE-ADA status for ITT Population during Period 2. The p-value associated

with the interaction term will be used to assess if the treatment groups effect is consistent across TE-ADA status groups. When the interaction term is statistically significant, the association between responder status and treatment groups depends, in some manner, on the status. The interaction will be tested at the 10% significance level. Treatment group differences will be evaluated within each TE-ADA subgroup using Fisher's exact test, regardless of whether the interaction is statistically significant.

6.14.11.2.3. Analyses of Treatment-Emergent ADA on Specific Adverse Events

The analyses of TE-ADA effects on safety will be conducted on all evaluable patients within the defined Safety Population for Period 2 and All Ixekizumab Population for combined Periods 2, 3, and 4.

Adverse events of special interest of allergic reaction/hypersensitivity (anaphylaxis and nonanaphylaxis) and of injection-site reactions will be included in an assessment of AE to TE-ADA over time. See Section 6.14.3.1 for the definitions of the AESIs. Timing of an AE will be taken to be the reported AE start date.

For each TE-ADA status dichotomous variable (as defined in Table RHCD.6.11), patients will be categorized according to whether they were: (1) always in lesser-TE-ADA status postbaseline; or (2) at some point postbaseline, were in greater-TE-ADA status. For each AESI, within the time-varying TE-ADA status groups, a summary will be provided of the number of patients who had no event, events only while in lesser-TE-ADA status for group (1), or – for group (2) – at least 1 event while in greater-TE-ADA status.

Additionally, summaries will be provided of the total number of AESI events (with unique start dates) by time-varying TE-ADA status groups at the event date. The summaries will aggregate time respectively in greater-TE-ADA status and in lesser-TE-ADA status, along with the event rates (rates per 100 patient-years) relative to those aggregate times.

By-patient listings will be provided of patients with TE-ADA who experience a treatment-emergent allergic reaction/hypersensitivity reaction or an injection site reaction.

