5.1. Summary of Study Design

Study I1F-MC-RHCD (RHCD) is a Phase 3, multicenter, double-blind, randomized, placebo-controlled study examining the effects of ixekizumab versus placebo in subjects from 6 to <18 years of age with moderate-to-severe plaque psoriasis (Ps) (Psoriasis Area and Severity Index [PASI] score ≥ 12 , static Physician's Global Assessment [sPGA] ≥ 3 , and body surface area [BSA] $\geq 10\%$ at screening and baseline). Protocol Addendum I1F-MC-RHCD(1) specifies the pharmacokinetics (PK) collection schedule and how the data from the approximately 24 subjects participating in the PK addendum will be used. Protocol Addendum I1F-MC-RHCD(2) specifies the details for the active-controlled (etanercept) portion of the study design, as well as a double-blind, randomized withdrawal period for subjects from European Union (EU) countries.

The study consists of 5 periods:

- **Period 1: Screening Period** (Visit 1) will assess subject eligibility and will occur approximately 7 to 30 days before Period 2 (baseline; Week 0; Visit 2).
- **Period 2: Double-Blind Treatment Period** (Induction Period) will occur from Week 0 (baseline; Visit 2) to Week 12 (Visit 7), comparing ixekizumab with placebo in a double-blind fashion. The dose of ixekizumab will not be adjusted during this period. Protocol Addendum I1F-MC-RHCD(2) describes etanercept as a reference control group for countries where etanercept is approved for treatment of chronic severe Ps in children and adolescents from the age of 6 years who are inadequately controlled by, or are intolerant to, other systemic therapies or phototherapies.
- **Period 3: 48-Week, Open-Label Maintenance Period** will occur from Week 12 (Visit 7) to Week 60 (Visit 19). Subjects randomized to the ixekizumab group during Period 2 will maintain the dose received during the previous period. Subjects randomized to placebo during Period 2 will receive ixekizumab at doses of 20, 40, or 80 mg, based on weight. As part of Protocol Addendum I1F-MC-RHCD(2), subjects randomized to etanercept during the Double-Blind Treatment Period will begin treatment with ixekizumab after an 8-week washout period (to avoid, for safety reasons, increased risk with concurrent etanercept and ixekizumab exposures). If a subject changes weight category following the Double-Blind Treatment Period, the ixekizumab dose associated with that weight will be administered. This may happen at any time during the Maintenance Period.

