- **Period 4: Extension Period** will occur from Week 60 (Visit 19) to Week 108 (Visit 31). Subjects will continue with open-label treatment of the ixekizumab dose received during the previous period (Period 3). Protocol Addendum I1F-MC-RHCD(2) describes the 48-week Double-Blind, Randomized Withdrawal Period for subjects from EU countries who meet response criteria during the Maintenance Period (defined as sPGA [0,1]). Subjects who enter the Double-Blind, Randomized Withdrawal Period will be re-randomized to ixekizumab or placebo (1:1 ratio) at Week 60 (Visit 19). Subjects who are re-randomized to

[figure not shown]
ixekizumab will receive ixekizumab 20, 40, or 80 mg every 4 weeks (Q4W) according to their weight at the time of re-randomization.

- **Period 5: Post-Treatment Follow-Up Period** is for safety monitoring after treatment discontinuation for any subject receiving at least 1 dose of study drug. This period occurs from the last treatment period visit or Early Termination Visit (ETV) for up to 24 weeks following that visit.

The underlined text in the following sections show the additions and deletions applicable to subjects participating in Protocol Addendum IIF-MC-RHCD(2).

- **Period 2: Double-Blind Treatment Period** (Induction Period) will occur from Week 0 (baseline; Visit 2) to Week 12 (Visit 7), comparing ixekizumab to placebo in a double-blind fashion (all countries) and to etanercept (as a reference arm – all countries except North America). The dose will remain the same in this treatment period.
- **Period 3: 48-Week, Open-Label Maintenance Period** will occur from Week 12 (Visit 7) to Week 60 (Visit 19). Subjects randomized to etanercept during Period 2 will receive ixekizumab at doses of 20, 40, or 80 mg, according to their weight after an etanercept 8-week washout period is complete. The etanercept washout period will be from Week 12 through Week 20. If a subject changes weight category following the Double-Blind Treatment Period, the ixekizumab dose associated with that weight will be administered. This may happen at any time during the Maintenance Period.

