- e Subjects will be randomized to receive etanercept 0.8 mg/kg and up to a maximum of 50 mg per dose. All subjects will receive etanercept SC Q1W at Week 0 through Week 11.
- f Unblinded site personnel will prepare the doses of ixekizumab and placebo.
- g Subjects will initiate Maintenance Period as follows: (1) Subjects randomized to the ixekizumab arm during Period 2 will receive 1 SC injection of ixekizumab and 1 SC injection of placebo at Week 12. (2) Subjects randomized to the placebo arm during Period 2 will be assigned to receive ixekizumab at doses of 20, 40, or 80 mg, according to weight, and will receive 2 ixekizumab injections as follows—subjects assigned to 20 mg will receive a starting dose of 40 mg; subjects assigned to 40 mg will receive a starting dose of 80 mg; subjects assigned to 80 mg will receive a starting dose of 160 mg. All subjects will receive 2 SC injections at Week 12. (3) Subjects randomized to etanercept during Period 2 will receive no injections at Weeks 12 and 16. At Week 20, subjects will be assigned to receive ixekizumab at doses of 20, 40, or 80 mg, according to their weight. Subjects assigned to 20 mg will receive a starting dose of 40 mg. Subjects assigned to 40 mg will receive a starting dose of 80 mg. Subjects assigned to 80 mg will receive a starting dose of 160 mg. Treatment with ixekizumab is weight-based. If a subject changes weight category during the study and after the Double-Blind Treatment Period, the dose will be adjusted accordingly.
- h All subjects will receive 1 SC injection of ixekizumab Q4W.
- i Subjects from EU countries who meet the response criterion at Week 60 (defined as sPGA [0,1]) will be re-randomized to ixekizumab or placebo (1:1 ratio). Subjects from EU countries who do not meet response criteria and subjects from non-EU countries will continue with open-label treatment with ixekizumab.
- j Subjects will receive ixekizumab upon disease relapse to Ps (sPGA ≥ 2).
- k All subjects receiving investigational product must enter into the Post-Treatment Follow-Up Period (Period 5) and complete through Visit 802. Subjects may be followed beyond Visit 802 for continued monitoring of their neutrophil counts if needed or if determined by the Sponsor/investigator that additional monitoring is needed.

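### Reaction rates by antibody status are crude with respect to time since the first ixekizumab dose, so the contrast can be biased in either direction

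*SAP*

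**What the plan says.** SAP section 6.14.11.2.3 relates allergic/hypersensitivity and injection-site reactions to antibody status over time. It counts events by the status in force on the event date and divides by the time spent in that status: "The summaries will aggregate time respectively in greater-TE-ADA status and in lesser-TE-ADA status, along with the event rates (rates per 100 patient-years". The analysis is run twice, for evaluable patients "within the defined Safety Population for Period 2 and All Ixekizumab Population for combined Periods 2, 3, and 4". No split or model term for time since the first ixekizumab dose is given, and section 6.1.3.3 keeps the combined periods descriptive.

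Two definitions decide which time counts as greater status.

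- Section 6.14.11.1.3: TE-ADA positivity needs a rise, either at least four-fold over a positive baseline or, "for a negative baseline titer, a patient with an increase from the baseline to a level of" 1:10 or more.
- Section 6.14.11.2: "the TE-ADA status is taken to be the highest of the TE-ADA values bracketing time" *t*. The later of the two bracketing values is "the TE-ADA status at the first TE-ADA postbaseline measurement at or after time" *t*. Before the first postbaseline sample, that sample's status is used.

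**The concern.** A patient whose first postbaseline sample is negative contributes the time up to that sample as lesser status, and enters greater status only after the last negative sample. If antibodies appear gradually, early treatment time therefore lies mostly in lesser status. The exception is a patient whose first postbaseline sample is already positive; all time before that sample then counts as greater status.

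Early doses also differ from later ones. Per the footnotes to SAP Figure RHCD.5.2, every weight group has a starting dose twice its later dose, and the 80 mg group has two injections at Week 0 and one at Weeks 4 and 8. This makes an early excess of injection-site reactions plausible but does not show one.

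If position in the treatment course is tied both to antibody status and to reaction risk, it confounds the comparison of the two crude rates. These are the plan's only event rates for reactions by antibody status, in a paediatric trial. A reader could take a ratio near or below 1 as reassurance, or a raised ratio as a signal, when either reflects timing.

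**Working it through.** The documents state no event count, reaction rate or power for this analysis, so there is no planned figure to reproduce.

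**Inputs from the documents (SAP section 5.1)**
- Period 2 "will occur from Week 0 (baseline; Visit 2) to Week 12 (Visit 7"); Period 4 "will occur from Week 60 (Visit 19) to Week 108 (Visit 31"). The combined span is 12 + 48 + 48 = 108 weeks.
- That span applies only to patients randomized to ixekizumab at Week 0. Placebo patients switch at Week 12, leaving 108 - 12 = 96 weeks. For the etanercept arm, "Subjects randomized to etanercept during Period 2 will receive no injections at Weeks 12 and 16"; ixekizumab starts at Week 20, leaving 108 - 20 = 88 weeks.

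**Assumptions not in the documents**
- Reaction rate of 10 per 100 patient-years after Week 12 and *k* times that in Weeks 0-12.
- Share *q* of each band's time spent in greater status.
- True rate ratio θ.

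**Two-band calculation, Weeks 0-12 and 12-108**

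Crude ratio = [θ Σ qTλ / Σ qT] ÷ [Σ (1-q)Tλ / Σ (1-q)T], where T is band length and λ the rate in lesser status.

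Take q = 2% early and 10% later, k = 5, θ = 1.5:
- Greater: 1.5 × (0.24 × 50 + 9.6 × 10) / 9.84 = 1.5 × 10.98 = 16.46.
- Lesser: (11.76 × 50 + 86.4 × 10) / 98.16 = 14.79.
- Crude ratio: 16.46 / 14.79 = 1.11.

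| Greater-status share, early / later | k | Crude ratio when truth is 1.5 | when truth is 2.0 |
|---|---|---|---|
| 2% / 10% | 2 | 1.37 | 1.83 |
| 2% / 10% | 5 | 1.11 | 1.48 |
| 2% / 10% | 10 | 0.88 | 1.17 |
| 5% / 5% | any | 1.50 | 2.00 |
| 10% / 5% | 5 | 1.90 | 2.53 |

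The Mantel-Haenszel rate ratio is Σ(a·L/N) / Σ(b·G/N). Here a and b are events in greater and lesser status, G and L the corresponding time, and N = G + L. For the worked case it is (18 × 11.76/12 + 144 × 86.4/96) / (588 × 0.24/12 + 864 × 9.6/96) = 147.24 / 98.16 = 1.50, the true value.

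**Period 2 alone, bands Weeks 0-4 and 4-12**

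Take the same 2% / 10% shares, k = 5 in Weeks 0-4, θ = 1.5:
- Greater: 1.5 × (0.08 × 50 + 0.8 × 10) / 0.88 = 20.45.
- Lesser: (3.92 × 50 + 7.2 × 10) / 11.12 = 24.10.
- Crude ratio: 0.85.

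**Simulation with the SAP's bracketing rule**

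This used 20,000 patients, 20% becoming positive, samples assumed at Weeks 4, 12, 24, 36, 60, 84 and 108, and a true ratio of 1.5.

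| Antibody appears | k (Weeks 0-12) | Crude | Stratified |
|---|---|---|---|
| Early (mean 8 weeks) | 5 / 10 | 1.28 / 1.16 | 1.46 / 1.44 |
| Uniform, Weeks 0-60 | 5 / 10 | 1.04 / 0.79 | 1.44 / 1.43 |
| Late, Weeks 12-108 | 5 / 10 | 0.94 / 0.66 | 1.41 / 1.41 |

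With uniform conversion and constant risk (k = 1), the crude ratio is 1.45. The remaining gap to 1.5 therefore comes mainly from misclassification by the bracketing rule, which stratifying does not remove. In Period 2 alone, with uniform conversion and a five-fold excess in Weeks 0-4, crude is 0.88 against 1.29 stratified.

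**Precision**

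Assume 110 + 55 + 30 = 195 patients (SAP sections 5.2.1 and 5.2.2), full follow-up and no time on withdrawal placebo.
- Exposure: 110 × 108 + 55 × 96 + 30 × 88 = 19,800 weeks, about 379 patient-years.
- In the worked case greater status holds 9.84/108 = 9.1%, about 34.6 patient-years and 5.7 events. Lesser status holds about 345 patient-years and 51 events.
- Standard error of the log ratio: √(1/5.7 + 1/51) = 0.44. A 95% interval spans a factor of about 2.4 each way.

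**The case against.** A reader might infer that the plan makes no allowance for time on treatment. The documents do not support that. Rates are per patient-year, status changes with time, so a converter's earlier negative time is not counted as positive outside the bracketing interval, and a separate 12-week run is planned. These features stand, but they address duration and change of status. The Period 2 figures above show that the shorter window can carry the same bias.

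The SAP also plans no rate ratio, test or decision rule here, so the contrast is one that readers will form for themselves. Companion outputs help. Section 6.14.11.2.3 gives patient counts by status group and listings of antibody-positive patients with reactions. Section 6.14.11.2.1 gives time to antibody development and a dated listing. Timing can be inspected case by case, but this does not adjust the rates.

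The strongest objection is that the bias needs two facts the documents do not supply: a change in reaction risk over treatment, and greater-status time falling at a different point from lesser-status time. That stands. So does the point on precision: the correction will be imprecise, most of all for anaphylaxis and the high-titer groups.

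**Conclusion.** Both sets of rates, for Period 2 and for Periods 2-4 combined, are crude with respect to position in the treatment course. The planned denominators and listings do not correct this. The direction is not fixed. With higher early risk, later greater-status time understates an antibody effect and can reverse it; earlier greater-status time exaggerates it; equal shares give no bias.

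A reader might go further and infer that the table will conceal a harmful antibody effect. The documents do not support that: they show neither an early excess of reactions nor late antibody development. In the illustrations, reversal needed a steep early excess or late conversion, and early conversion gave attenuation only. Every magnitude shown rests on assumed rates, shares, sampling weeks and incidence.

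The table is descriptive, and the gatekeeping in section 6.5 is untouched. This is a minor-to-moderate improvement to a safety analysis.

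**What to change.** In section 6.14.11.2.3, for injection-site reactions and for all allergic/hypersensitivity events, using the TE-ADA-positive variable:

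- Also present events, person-time and rates by status within a few coarse intervals since the start of the current ixekizumab exposure period, for example Weeks 0-4, >4-12 and >12.
- Give one Mantel-Haenszel rate ratio stratified by interval, with a 95% confidence interval.
- State how a second ixekizumab exposure after placebo withdrawal is counted. Sections 6.1.2 and 6.14.1 recognise two exposure periods for these patients, but this analysis has no rule for them.
- Keep the crude rates as description.

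The cost is SAP wording and one interval variable, since adverse events are already placed by start date. The downsides are sparse cells and wide intervals, which is why the request is limited to the broadest antibody variable and event groups. Misclassification from the bracketing rule remains and should be stated beside the table.
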